7.10.2. Day 1 (Study Drug Administration)

Dosing

PUL-042 administration must be supervised by a health care professional. PUL-042 will be administered via a PARI Sprint nebulizer equipped with a filter valve to prevent aerosol generation. A nose clip will be used during the nebulization procedure. All doses will be administered as a constant volume (4 mL) via nebulization; the nebulizer will be operated until all drug has been delivered. All of the following time points are defined relative to the completion of dosing (T_0).

Post-Dose Guidelines

In previous studies with healthy volunteers, some subjects have demonstrated a transient decrease in lung function, usually asymptomatic. To date, subjects have recovered to at or near baseline lung function values without the administration of rescue medication. However, if after administration of PUL-042 Inhalation Solution there are clinical symptoms (increased respiratory rate, cough, shortness of breath) of decreased lung function, albuterol (salbtuamol) can be administered.

Following dosing, if a reduction of FEV1 >10% relative to pre-treatment is recorded, the subject should have the FEV1 measurement repeated as clinically indicated. If a reduction of FEV1 >12% relative to pre-treatment is recorded at 4 hours, the subject must be reviewed by the Principal Investigator prior to further dosing. If a reduction of FEV1 >12% relative to pre-treatment persists for up to 4 hours and is associated with clinical symptoms over this period, no further investigational treatment should be administered. Albuterol (salbutamol) may be given to symptomatic subjects at the discretion of the investigator.

If a reduction of FEV1 >20% relative to pre-treatment is recorded, no further investigational treatment should be administered to that subject.

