12. ADVERSE EVENTS

Adverse events will be described and graded according to the Toxicity Grading Scale for Healthy Adult and Adolescent Volunteers Enrolled in Preventive Vaccine Clinical Trials.

Symptoms and events associated with SARS-CoV-2 infection will be scored as per the SARS-CoV-2 infection symptom score (Table 2) and the Ordinal Scale for Clinical Improvement (Table 4). These findings should not be reported as Adverse Events.

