An AE is classified as "serious" based on the criteria outlined below. Seriousness (not severity) defines the regulatory reporting obligations.

An adverse event or suspected adverse reaction is considered "serious" if in the view of either the investigator or sponsor, it results in any of the following outcomes:

- Death
- A life-threatening adverse event
- In-patient hospitalization or prolongation of existing hospitalization
- Persistent or significant incapacity or substantial disruption to conduct normal life functions
- A congenital anomaly/birth defect
- Intervention to prevent any one of the other outcomes listed above (based on medical judgment)

Important medical events that may not result in death, be life-threatening, or require hospitalization may be considered serious when, based on appropriate medical judgment, they may jeopardize the subject and may require medical or surgical intervention to prevent one of the outcomes listed above. Examples of such medical events are allergic bronchospasm requiring intensive treatment in the emergency room or at home, blood dyscrasias, convulsions that do not result in in-patient hospitalization, or the development of drug dependency or drug abuse.

Unexpected Adverse Event or Unexpected Suspected Adverse Reaction

An AE or suspected adverse reaction is considered "unexpected" if it is not listed in the Investigator's Brochure or is not listed in the Investigator's Brochure at the specificity and severity observed.

Serious and Unexpected Adverse Event or Suspected Adverse Reaction

Any AE or suspected adverse reaction that occurs during the subject's participation in the study that meets the criteria for both serious and unexpected as defined above is considered a serious and unexpected AE or suspected adverse reaction.

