12.6. Reporting Serious or Unexpected AEs

Any SAE or serious suspected adverse reaction that occurs during the course of the study will be reported within 24 hours after the site becomes aware of the event.

All SAE reporting will adhere to the United States Code of Federal Regulations (CFR), specifically 21 CFR 312.32 for Investigational New Drugs, and applicable local regulations. The Investigator will notify the governing IRB or Ethics Committee of any SAEs and safety reports per IRB or Ethics Committee reporting requirements.

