13.3. Primary Objective

To determine the efficacy of PUL-042 Inhalation Solution in the prevention of viral infection with SARS-CoV-2 and progression to COVID-19 in subjects: 1) who have repeated exposure to individuals with SARS-COV-2 infection and 2) who are asymptomatic at enrollment.

The primary endpoint is the severity of COVID-19 as measured by the maximum difference from the baseline value in the Ordinal Scale for Clinical Improvement within 28 days from the start of experimental therapy. The Ordinal Scale for Clinical Improvement is a 9-point scale that measures disease severity at a given point in time. Notably, a score of 0 indicates that an individual is infection-free. The difference in scores obtained at different times provides a quantitative assessment of the incidence of infection and change in disease severity over that time interval. The change in severity between the placebo- and actively-treated groups will be analyzed by a linear statistical model adjusting for the main effect of randomized treatment and other relevant covariates (e.g., age, baseline OSCI Score, and presence of comorbidities). Because the statistical properties of these score differences might not conform to the theoretical requirements of this procedure, a Wilcoxon Rank-Sum (nonparametric) test may also be used to analyze the main effect of treatment. Full details of the planned analysis will be included in the Statistical Analysis Plan that will be developed for this study.

The Ordinal Scale for Clinical Improvement to be used in this study is derived from a draft scale proposed by the World Health Organization⁹ for clinical improvement as presented below in Table 4:

Descriptor	Score	
No clinical or virological evidence of infection	0	
Infected but no limitation of activities	1	
Limitation of activities	2	
Hospitalized not requiring oxygen therapy (SpO2 > 93% on room air)	3	
Oxygen by mask or nasal prongs	4	
Non-invasive ventilation or high-flow oxygen	5	
Intubation and mechanical ventilation	6	
Ventilation + additional organ support- pressors, RRT, ECMO	7	
Death	8	

Table 4:Ordinal Scale for Clinical Improvement (Derived from draft WHO scale)

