14.4. Data Safety Monitoring Board

An external DSMB will be used to evaluate safety of the study in an ongoing manner. There will be three voting members. None of the voting members will have any affiliation with Pulmotect, Inc. A full description of the membership, role, and responsibilities of the DSMB will be finalized prior to the start of the study, and will be provided in the DSMB charter. The DSMB will evaluate safety at regular intervals including early in the trial.

The DSMB chair has the ability to pause study enrollment at any point during the study for any reason including rapid enrollment which could hinder the DSMB's ability to review the safety of PUL-042 Inhalation Solution in a timely manner relative to overall enrollment. The first evaluation will be done after 40 subjects have completed dosing. Unless the DSMB recommends to the contrary, enrollment will be allowed to continue until 80 patients have completed dosing. Enrollment beyond 80 subjects will require formal DSMB review of the data from the first 40 subjects to have been completed with explicit approval to continue enrollment beyond 80 subjects. Subsequent evaluations will occur at 120 patients with further ad hoc meetings at the discretion of the DSMB.

One potential recommendation of the DSMB is to stop the study due to safety concerns. Any imbalance in the incidence of AEs between placebo and active treatment is to be further reviewed by the DSMB taking into account the totality of evidence in order to render a recommendation to the sponsor regarding study continuation. As specified in the DSMB charter the formal review of data will take place at each meeting of the DSMB after 40, 80 and 120 subjects have completed dosing. Ad hoc meetings can also be called.

As a further effort to ensure the safety of PUL-042, a stopping rule that is based only on mortality will be employed. This rule will be implemented if there is a high probability of excess mortality risk among patients randomized to PUL-042. The following hierarchical analysis of mortality will be performed after 50% of subjects have been enrolled (50/group) and followed up for 28 days from the start of investigational therapy:

1) Based on blinded data, if no more than 3 deaths have occurred during the study this analysis will not be conducted due to the lack of evidence of increased mortality risk attributable to PUL-042.

If more than 3 deaths occur:

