7.2.5 Adverse Event Summaries

All AEs (serious and non-serious) occurring after randomization and before the end of study, regardless of relationship to study drug, will be included and classified by SOC and PT using MedDRA.

For TEAEs, the following will be summarized and presented:

- i. An overall summary of TEAEs, which includes:
 - a. the number and percentage of subjects experiencing a TEAE
 - b. the number and percentage of subjects experiencing a TEAE by strongest relationship to study drug
 - c. the number and percentage of subjects experiencing a TEAE by greatest severity
 - d. the number and percentage of subjects experiencing a treatment-emergent SAE
 - e. the number and percentage of subjects experiencing a TEAE leading to death
 - f. the number and percentage of subjects experiencing a TEAE leading to study withdrawal
- ii. the number and percentage of subjects experiencing a TEAE by SOC and PT.
- iii. the number and percentage of subjects experiencing a potentially related TEAE by SOC and PT, where a potentially related TEAE is defined as any TEAE with a causal relationship to study drug assessed as 'Possibly Related', 'Probably Related', or 'Definitely Related'.
- iv. the number and percentage of subjects experiencing a TEAE by SOC, PT and the strongest relationship to study drug
- v. the number and percentage of subjects experiencing a TEAE by SOC, PT and the greatest severity
- vi. the number and percentage of subjects experiencing a treatment-emergent SAE by SOC and PT
- vii. the number and percentage of patients experiencing a TEAE leading to death by SOC and PT
- viii. the number and percentage of subjects experiencing a TEAE leading to study withdrawal by SOC and PT

In the overall summary of TEAEs table (i), besides tabulating the number and percentage of subjects, the total number of TEAE episodes will also be provided. If a subject has repeated episodes of a particular TEAE, all episodes will be counted in the summary table.

In the remaining summary tables, the incidence of TEAEs will be calculated by dividing the number of subjects who have experienced the event by the total number of subjects. Thus, the incidence of TEAEs is shown in terms of the total number of subjects and not in terms of the total number of episodes. If a subject has repeated episodes of a particular TEAE, only the most severe episode, or the episode with the strongest causal relationship to study drug, will be counted in the summary tables.

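### The AE exemption for SARS-CoV-2 events makes no exception for serious ones, and neither document commits the DSMB to review non-fatal serious COVID-19 by arm

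*Protocol*

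**What the plan says.** Protocol Section 12, repeated as a note in 12.4, directs that symptoms and events associated with SARS-CoV-2 infection be scored on the symptom score (Table 2) and the ordinal scale (Table 4). It then says: "These findings should not be reported as Adverse Events". Neither place makes an exception for seriousness or requires a positive test.

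Table 4, in Section 13.3, starts its hospital categories at score 3, "Hospitalized not requiring oxygen therapy", and runs through ventilation (6 and 7) to death (8). Section 12.1 counts death and "In-patient hospitalization or prolongation of existing hospitalization" among the outcomes that make an adverse event serious. Section 12.6 states: "Any SAE or serious suspected adverse reaction that occurs during the course of the study will be reported within 24 hours" of the site becoming aware.

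On oversight, Section 14.4 says: "Any imbalance in the incidence of AEs between placebo and active treatment is to be further reviewed by the DSMB". It adds a mortality rule: one analysis at 50 per group after 28 days of follow-up, run only if more than 3 deaths have occurred, and met when the death rate on PUL-042 exceeds placebo by more than 7.5%. Section 13.5 lists the data for ongoing safety review: TEAEs, vital signs, physical examinations, laboratory data, lung function and noncompliance.

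SAP 7.2.5 builds its tables from TEAEs, including "the number and percentage of subjects experiencing a treatment-emergent SAE" and TEAEs leading to death. SAP Section 7 does not mention the exemption.

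**The concern.** An event must first be recorded as an AE before it can be an SAE. A COVID-19 admission that meets the seriousness criteria is therefore removed before seriousness is considered. The SAE tables will look complete to a reader of the SAP but will omit these events.

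This matters because PUL-042 stimulates innate immunity in the lung and is given to people who are exposed to the virus; Section 7.8 allows dosing to continue after a positive test. If treatment made infection more severe, the excess admissions would not count towards the AE imbalance that the DSMB is told to review, and the prespecified mortality rule looks only at deaths.

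There is also a smaller attribution problem. Cough and shortness of breath are Table 2 items, and the post-dose guidelines in Sections 7.10.2 and 7.11.2 name them as "clinical symptoms (increased respiratory rate, cough, shortness of breath) of decreased lung function". No rule says when such a symptom counts as infection-associated and so leaves the AE record.

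**Working it through.** **1. Where a COVID-19 admission goes under the current text**

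| Route | Source | Reached? |
|---|---|---|
| AE record | Protocol 12, 12.4 | No, exempt |
| 24-hour SAE report | Protocol 12.6 | No, not an AE |
| SAE and fatal-TEAE tables | SAP 7.2.5 | No, built from TEAEs |
| AE-imbalance review | Protocol 14.4 | No, worded in AEs |
| Ongoing safety review list | Protocol 13.5 | Ordinal scale not named |
| Mortality rule | Protocol 14.4, SAP 8 | Only if fatal |
| Efficacy tables by arm | SAP 6.1, 6.2 | Yes |
| DSMB data package | Protocol 11.1, 14.4 | Contents not stated |

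**2. The plan's own figures for the mortality rule**

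Inputs from Protocol 14.4 and SAP 8: control mortality 5%, threshold 7.5%, 50 per group, normal approximation. Stated probabilities are 90%, 62% and 11% for PUL-042 mortality of 25%, 15% and 5%.

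Formula: P = 1 − Φ[(0.075 − (pA − pC)) / SE], with SE = √[pA(1 − pA)/n + pC(1 − pC)/n].

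At n = 50 and pA = 0.15: SE = √[(0.1275 + 0.0475)/50] = 0.0592, z = (0.075 − 0.10)/0.0592 = −0.423, P = 66.4%.

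| PUL-042 mortality | Stated | n = 50 per group | n = 25 per group |
|---|---|---|---|
| 25% | 90% | 96.6% | 90.1% |
| 15% | 62% | 66.4% | 61.7% |
| 5% | 11% | 4.3% | 11.2% |

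The stated figures fit 25 per group, not the 50 per group written beside them. That is a separate matter. The calculation below uses 50 per group.

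**3. Can the mortality rule stand in for non-fatal harm?**

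At 50 per group, 7.5% is 3.75 subjects, so the rule needs at least 4 more deaths on PUL-042. I computed two exact binomial probabilities:

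- Hospitalisation: the observed excess on PUL-042 is above 7.5 points.
- Mortality rule: the death-rate excess is above 7.5 points and there are at least 4 deaths in total. Each arm's death rate is its hospitalisation rate times the fatality among those cases.

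The documents give no hospitalisation or fatality rates, so all of these are assumptions, shown as a range.

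| Hospitalised, placebo vs PUL-042 | Excess seen if tabulated | Rule met, 10% fatal | Rule met, 20% fatal |
|---|---|---|---|
| 2% vs 8% | 0.39 | 0.001 | 0.007 |
| 5% vs 10% | 0.34 | 0.001 | 0.012 |
| 5% vs 15% | 0.69 | 0.005 | 0.043 |
| 5% vs 20% | 0.90 | 0.014 | 0.10 |

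In every row a by-arm count is far more likely to show the excess than the mortality rule is to be met.

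**The case against.** The strongest reply is that nothing is lost, only filed elsewhere. The ordinal scale is the primary endpoint and is tested two-sided, so harm lies within the alternative hypothesis. SAP 6.2 gives the number and percentage in each ordinal category by visit and arm, and compares ICU admission, ventilation and all-cause mortality by arm. Treating disease events as endpoints rather than AEs avoids double recording. All of this stands, and it is why the point concerns safety reporting and interim oversight rather than lost data.

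A reader might infer that deaths or severe cases are hidden from the DSMB. The documents do not support that. Deaths enter the mortality rule whatever their AE status. The board reviews unblinded data at 40, 80 and 120 subjects, may meet ad hoc, and weighs the totality of evidence. SAP Section 1 says that its methods also cover the DSMB analysis. Which tables the board receives is not stated, and the charter is not among the documents, so neither inclusion nor omission of the ordinal scale can be asserted.

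A reader might also infer that acute drug reactions will be written off as COVID-19. That goes too far. The 30-minute post-dose visit schedules an AE assessment and spirometry but no symptom score, FEV1 falls are tabulated by arm, and testing is called for when symptoms suggest COVID-19. Only the lack of an attribution rule remains.

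Calling this the most serious harm the drug could cause would be a judgement that the documents do not make. Nor would every imbalance be conclusive: an assumed 5 of 100 versus 10 of 100 gives a Fisher p of 0.28, and at the first review, with about 20 per arm, the same rates are about 1 versus 2 events.

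**Conclusion.** The point holds in this form. The exemption in Protocol 12 and 12.4 has no exception for serious events, so it conflicts in effect with 12.1 and 12.6. It removes COVID-19 hospitalisation, ventilation and death from SAE reporting, the SAP 7.2.5 tables and the AE-imbalance review. Neither document replaces those routes with a committed by-arm DSMB review of non-fatal serious COVID-19.

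The removal follows from the wording and needs no assumption. The size of the oversight gap does rest on assumptions: for hospitalisation of 5% versus 15% with 10% to 20% fatal, the mortality rule is met with probability 0.005 to 0.043, against 0.69 for seeing the excess in a table; across the rates tried, 0.001 to 0.10 against 0.34 to 0.90. If the charter already puts ordinal-scale tables in each DSMB package, the interim gap closes in practice. The incomplete SAE tables and the conflict between sections would remain. This should be changed; it does not invalidate the efficacy analysis.

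**What to change.** - **SAP 7 and 8:** add a by-arm table of subjects with ordinal score 3 or more, ICU admission, mechanical ventilation and death to each DSMB review (40, 80 and 120 subjects) and to the final safety tables.
- **Protocol 14.4:** extend the imbalance review from AEs to these events.
- **SAP 7.2.5:** footnote the SAE and fatal-TEAE tables to say that infection-associated events are excluded and where they are reported.
- **Protocol 12 and 12.4:** reconcile with 12.1 and 12.6 by stating how serious infection-associated events are reported. For the exemption, treat a symptom as infection-associated only with a positive SARS-CoV-2 test.

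Recording every serious endpoint event as an SAE is one way to reconcile the sections. It brings duplicate recording and 24-hour reports, and the table does not depend on it.

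The cost is a protocol amendment for the wording and one extra table per review, built from data already collected. Endpoint events will be shown twice, under efficacy and under safety.

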12.1. Definitions

Adverse Event (AE)

An AE is any untoward medical occurrence associated with the use of a drug in humans, whether or not considered drug related.

An AE can therefore be any unfavorable and unintended sign (including an abnormal laboratory finding, for example), symptom, or disease temporally associated with the use of a medicinal (investigational) product, whether or not related to the medicinal (investigational) product.

An abnormal laboratory value will be considered an AE if it qualifies as such based on the Toxicity Grading Scale for Healthy Adult and Adolescent Volunteers Enrolled in Preventive Vaccine Clinical Trials.

Throughout the course of the study, every effort should be made to remain alert to possible AEs. Subjects should be encouraged to report AEs spontaneously or in response to general, nondirected questioning.

With the occurrence of an AE, the primary concern is the safety of the subject. Appropriate management of the AE should always be the first priority.

Suspected Adverse Reaction

Defined as any adverse event for which there is a reasonable possibility that the drug caused the adverse event. For the purposes of IND safety reporting "reasonable possibility" means there is evidence to suggest a causal relationship between the drug and the adverse event. Suspected adverse reaction implies a lesser degree of certainty about causality than adverse reaction, which means any adverse event caused by the drug.

Life-Threating Adverse Event or Life-Threatening Suspected Adverse Reaction

An adverse event or suspected adverse reaction is considered "life-threatening" if, in the view of either the investigator or sponsor, its occurrence places the patient or subject at immediate risk of death. It does not include an adverse event or suspected adverse reaction that, had it occurred in a more severe form might have caused death.

Serious Adverse Event (SAE) or Serious Suspected Adverse Reaction

The terms "serious" and "severe" are not synonymous. Adverse events classified as "serious" have defined regulatory requirements. Those classified as "severe" do not have defined regulatory requirements unless they are also classified as "serious".

The term "severe" is often used to describe the intensity of a specific event (as in mild, moderate, or severe myocardial infarction); the event itself, however, may be of relatively minor medical significance (such as severe headache).

An AE is classified as "serious" based on the criteria outlined below. Seriousness (not severity) defines the regulatory reporting obligations.

An adverse event or suspected adverse reaction is considered "serious" if in the view of either the investigator or sponsor, it results in any of the following outcomes:

- Death
- A life-threatening adverse event
- In-patient hospitalization or prolongation of existing hospitalization
- Persistent or significant incapacity or substantial disruption to conduct normal life functions
- A congenital anomaly/birth defect
- Intervention to prevent any one of the other outcomes listed above (based on medical judgment)

Important medical events that may not result in death, be life-threatening, or require hospitalization may be considered serious when, based on appropriate medical judgment, they may jeopardize the subject and may require medical or surgical intervention to prevent one of the outcomes listed above. Examples of such medical events are allergic bronchospasm requiring intensive treatment in the emergency room or at home, blood dyscrasias, convulsions that do not result in in-patient hospitalization, or the development of drug dependency or drug abuse.

Unexpected Adverse Event or Unexpected Suspected Adverse Reaction

An AE or suspected adverse reaction is considered "unexpected" if it is not listed in the Investigator's Brochure or is not listed in the Investigator's Brochure at the specificity and severity observed.

Serious and Unexpected Adverse Event or Suspected Adverse Reaction

Any AE or suspected adverse reaction that occurs during the subject's participation in the study that meets the criteria for both serious and unexpected as defined above is considered a serious and unexpected AE or suspected adverse reaction.

